**Transient Ischemic Attack - Galapagos Search Term List**

**MedDRA Version 25.0**

TERM_CODE	TERM_NAME	TERM_TYPE
10006127	Brain hypoxia	PT
10006147	Brain stem infarction	PT
10006148	Brain stem ischaemia	PT
10008034	Cerebellar infarction	PT
10008118	Cerebral infarction	PT
10008120	Cerebral ischaemia	PT
10008190	Cerebrovascular accident	PT
10014498	Embolic stroke	PT
10019005	Haemorrhagic cerebral infarction	PT
10019016	Haemorrhagic stroke	PT
10028047	Moyamoya disease	PT
10043647	Thrombotic stroke	PT
10044390	Transient ischaemic attack	PT
10050209	Spinal cord ischaemia	PT
10050496	Reversible ischaemic neurological deficit	PT
10051078	Lacunar infarction	PT
10053841	Sneddon's syndrome	PT
10055677	Haemorrhagic transformation stroke	PT
10056237	Migrainous infarction	PT
10057375	Balint's syndrome	PT
10058571	Spinal cord infarction	PT
10058842	Cerebrovascular insufficiency	PT
10059613	Stroke in evolution	PT
10060839	Embolic cerebral infarction	PT
10060840	Ischaemic cerebral infarction	PT
10061256	Ischaemic stroke	PT
10064961	Thalamic infarction	PT
10065528	NIH stroke scale score increased	PT
10065531	NIH stroke scale abnormal	PT
10067347	Thrombotic cerebral infarction	PT
10067744	Capsular warning syndrome	PT
10068621	Cerebellar ischaemia	PT
10068644	Brain stem stroke	PT
10069020	Basal ganglia infarction	PT
10070511	Hypoxic-ischaemic encephalopathy	PT

GLPG0634-CL-MACE, 20DEC22:15:49

---

**Transient Ischemic Attack - Galapagos Search Term List**

**MedDRA Version 25.0**

---

TERM_CODE	TERM_NAME	TERM_TYPE
10070671	Cerebral septic infarct	PT
10070878	Cerebral small vessel ischaemic disease	PT
10071043	Basal ganglia stroke	PT
10073945	Perinatal stroke	PT
10075401	Cerebral reperfusion injury	PT
10076994	Lacunar stroke	PT
10078202	Post cardiac arrest syndrome	PT
10078388	Delayed ischaemic neurological deficit	PT
10079062	Cerebellar stroke	PT
10080347	Extracerebral cerebral haematoma	PT
10080713	Hemihyperaesthesia	PT
10082031	Spinal stroke	PT
10082484	Vertebrobasilar stroke	PT
10082594	Foville syndrome	PT
10083174	Hemidysaesthesia	PT
10083408	Internal capsule infarction	PT
10083668	Cerebral microinfarction	PT
10084072	Embolic cerebellar infarction	PT

---

GLPG0634-CL-MACE, 20DEC22:15:49

**Stroke - Galapagos Search Term List**

**MedDRA Version 25.0**

TERM_CODE	TERM_NAME	TERM_TYPE
10006145	Brain stem haemorrhage	PT
10006147	Brain stem infarction	PT
10008030	Cerebellar haemorrhage	PT
10008034	Cerebellar infarction	PT
10008111	Cerebral haemorrhage	PT
10008118	Cerebral infarction	PT
10008120	Cerebral ischaemia	PT
10008190	Cerebrovascular accident	PT
10014498	Embolic stroke	PT
10018985	Haemorrhage intracranial	PT
10019005	Haemorrhagic cerebral infarction	PT
10019013	Haemorrhagic infarction	PT
10019016	Haemorrhagic stroke	PT
10022775	Intracranial tumour haemorrhage	PT
10022840	Intraventricular haemorrhage	PT
10030936	Optic nerve infarction	PT
10035092	Pituitary infarction	PT
10042316	Subarachnoid haemorrhage	PT
10043647	Thrombotic stroke	PT
10044390	Transient ischaemic attack	PT
10048992	Spinal cord haemorrhage	PT
10049236	Spinal epidural haemorrhage	PT
10049760	Pituitary haemorrhage	PT
10051078	Lacunar infarction	PT
10055677	Haemorrhagic transformation stroke	PT
10057403	Choroidal infarction	PT
10058571	Spinal cord infarction	PT
10058939	Thalamus haemorrhage	PT
10058940	Putamen haemorrhage	PT
10059613	Stroke in evolution	PT
10060839	Embolic cerebral infarction	PT
10060840	Ischaemic cerebral infarction	PT
10061256	Ischaemic stroke	PT
10063176	Prosthetic cardiac valve thrombosis	PT
10064961	Thalamic infarction	PT

GLPG0634-CL-MACE, 20DEC22:15:49

**Stroke - Galapagos Search Term List**

**MedDRA Version 25.0**

TERM_CODE	TERM_NAME	TERM_TYPE
10067057	Basal ganglia haemorrhage	PT
10067347	Thrombotic cerebral infarction	PT
10067744	Capsular warning syndrome	PT
10068644	Brain stem stroke	PT
10069020	Basal ganglia infarction	PT
10070671	Cerebral septic infarct	PT
10071043	Basal ganglia stroke	PT
10072043	Central nervous system haemorrhage	PT
10073563	Spinal subdural haemorrhage	PT
10073564	Spinal subarachnoid haemorrhage	PT
10077193	Hemihypoaesthesia	PT
10080347	Extracerebral cerebral haematoma	PT
10082031	Spinal stroke	PT
10082484	Vertebrobasilar stroke	PT
10083006	Eye infarction	PT
10083087	Fluorescence angiogram abnormal	PT
10083408	Internal capsule infarction	PT
10083668	Cerebral microinfarction	PT
10083691	Lambert's excrescences	PT
10084072	Embolic cerebellar infarction	PT
10085447	Claude's syndrome	PT
10085448	Weber's syndrome	PT
10085451	Benedikt's syndrome	PT
10085944	Haemorrhagic cerebellar infarction	PT
10086546	Malignant middle cerebral artery syndrome	PT
10086596	Metabolic stroke	PT
10087275	Heidelberg classification	PT

GLPG0634-CL-MACE, 20DEC22:15:49

**Cardiac Failure - Galapagos Search Term List**

**MedDRA Version 25.0**

TERM_CODE	TERM_NAME	TERM_TYPE
10007554	Cardiac failure	PT
10007556	Cardiac failure acute	PT
10007558	Cardiac failure chronic	PT
10007559	Cardiac failure congestive	PT
10007560	Cardiac failure high output	PT
10007577	Cardiac index decreased	PT
10007595	Cardiac output decreased	PT
10007625	Cardiogenic shock	PT
10010968	Cor pulmonale	PT
10010969	Cor pulmonale acute	PT
10010970	Cor pulmonale chronic	PT
10013012	Dilatation ventricular	PT
10024119	Left ventricular failure	PT
10024899	Low cardiac output syndrome	PT
10031123	Orthopnoea	PT
10039163	Right ventricular failure	PT
10049632	Oedema due to cardiac disease	PT
10049694	Left ventricular dysfunction	PT
10050528	Ejection fraction decreased	PT
10051093	Cardiopulmonary failure	PT
10052337	Diastolic dysfunction	PT
10053405	Brain natriuretic peptide increased	PT
10053408	Brain natriuretic peptide abnormal	PT
10058597	Right ventricular dysfunction	PT
10059056	Ventricular dysfunction	PT
10060953	Ventricular failure	PT
10063081	Acute left ventricular failure	PT
10063082	Acute right ventricular failure	PT
10063083	Chronic left ventricular failure	PT
10063084	Chronic right ventricular failure	PT
10068230	Cardiorenal syndrome	PT
10069140	Myocardial depression	PT
10071436	Systolic dysfunction	PT
10071660	N-terminal prohormone brain natriuretic peptide abnormal	PT
10071662	N-terminal prohormone brain natriuretic peptide increased	PT

GLPG0634-CL-MACE, 20DEC22:15:49

**Cardiac Failure - Galapagos Search Term List**

**MedDRA Version 25.0**

---

TERM_CODE	TERM_NAME	TERM_TYPE
10075337	Right ventricular ejection fraction decreased	PT
10077781	Prohormone brain natriuretic peptide increased	PT
10077783	Prohormone brain natriuretic peptide abnormal	PT
10079613	Right ventricular diastolic collapse	PT
10079751	Cardiac dysfunction	PT
10080987	Left ventricular diastolic collapse	PT
10080992	Ventricular compliance decreased	PT
10082615	Coronary sinus dilatation	PT
10084058	Congestive hepatopathy	PT
10086295	Myocardial strain imaging abnormal	PT
10086620	Dynamic cardiomyoplasty	PT
10086706	Cardiac contractility decreased	PT

---

GLPG0634-CL-MACE, 20DEC22:15:49

**Percutaneous Coronary Intervention - Galapagos Search Term List**

**MedDRA Version 25.0**

---

TERM_CODE	TERM_NAME	TERM_TYPE
10002475	Angioplasty	PT
10003140	Arterectomy with graft replacement	PT
10003144	Arterial aneurysm repair	PT
10003148	Arterial catheterisation	PT
10003190	Arteriovenous fistula operation	PT
10007692	Carotid endarterectomy	PT
10011077	Coronary artery bypass	PT
10011090	Coronary artery surgery	PT
10011101	Coronary endarterectomy	PT
10014648	Endarterectomy	PT
10014649	Endarterectomy of aorta	PT
10022736	Intra-cerebral aneurysm operation	PT
10043530	Thrombectomy	PT
10043568	Thrombolysis	PT
10048932	Vena cava filter insertion	PT
10049071	Vascular operation	PT
10049887	Coronary revascularisation	PT
10050329	Coronary angioplasty	PT
10052086	Coronary arterial stent insertion	PT
10052371	Ventricular assist device insertion	PT
10052681	Valvuloplasty cardiac	PT
10052698	Catheterisation venous	PT
10052928	Clamping of blood vessel	PT
10052949	Arterial therapeutic procedure	PT
10052964	Venous repair	PT
10052989	Intra-aortic balloon placement	PT
10053003	Carotid artery bypass	PT
10053351	Peripheral revascularisation	PT
10053494	Aneurysmectomy	PT
10056418	Arterial bypass operation	PT
10057335	Therapeutic embolisation	PT
10057493	Renal artery angioplasty	PT
10057518	Peripheral artery angioplasty	PT
10057617	Aortic bypass	PT
10058408	Surgical vascular shunt	PT

---

GLPG0634-CL-MACE, 20DEC22:15:49

**Percutaneous Coronary Intervention - Galapagos Search Term List**

**MedDRA Version 25.0**

TERM_CODE	TERM_NAME	TERM_TYPE
10058794	Vasodilation procedure	PT
10059676	Arteriovenous graft	PT
10061656	Arterial repair	PT
10061657	Arterial stent insertion	PT
10062175	Venous operation	PT
10063025	Atherectomy	PT
10063170	Pulmonary artery banding	PT
10063382	Vascular stent insertion	PT
10063389	Venous stent insertion	PT
10063731	Pulmonary artery therapeutic procedure	PT
10064727	Renal artery stent placement	PT
10064778	Venous ligation	PT
10064958	Thromboembolectomy	PT
10065608	Percutaneous coronary intervention	PT
10066050	Aneurysm repair	PT
10066102	Carotid artery stent insertion	PT
10066129	Arterial switch operation	PT
10067740	Vascular graft	PT
10068628	Prosthetic vessel implantation	PT
10069948	Renal artery stent removal	PT
10069949	Vascular stent removal	PT
10069950	Arterial stent removal	PT
10069952	Carotid artery stent removal	PT
10069953	Coronary artery stent removal	PT
10071026	Arterectomy	PT
10071256	Aortic stent insertion	PT
10071260	Carotid angioplasty	PT
10071261	Mesenteric artery stent insertion	PT
10071508	Cerebral revascularisation	PT
10072559	Carotid revascularisation	PT
10072560	Peripheral endarterectomy	PT
10072561	Peripheral artery bypass	PT
10072562	Peripheral artery stent insertion	PT
10072893	Pulmonary endarterectomy	PT
10073598	Vascular anastomosis	PT

GLPG0634-CL-MACE, 20DEC22:15:49

**Percutaneous Coronary Intervention - Galapagos Search Term List**

**MedDRA Version 25.0**

---

TERM_CODE	TERM_NAME	TERM_TYPE
10074169	Vascular catheterisation	PT
10074397	Vena cava filter removal	PT
10075134	Prosthetic vessel removal	PT
10077079	Cerebral endovascular aneurysm repair	PT
10077826	Venous angioplasty	PT
10078636	Arteriotomy	PT
10081419	Vessel harvesting	PT
10081731	Arterial angioplasty	PT
10083018	Vascular ligation	PT
10084091	Revascularisation procedure	PT
10084482	Arterial revascularisation	PT
10084745	Temporary mechanical circulatory support	PT
10084977	Cardiac catheter removal	PT
10085325	Catheter directed thrombolysis	PT

---

GLPG0634-CL-MACE, 20DEC22:15:49

**Specific AE directly associated with the pathogen causing COVID-19 - Galapagos Search Term List**

**MedDRA Version 25.0**

TERM_CODE	TERM_NAME	TERM_TYPE
10051905	Coronavirus infection	PT
10070255	Coronavirus test positive	PT
10084268	COVID-19	PT
10084271	SARS-CoV-2 test positive	PT
10084380	COVID-19 pneumonia	PT
10084381	Coronavirus pneumonia	PT
10084459	Asymptomatic COVID-19	PT
10084460	COVID-19 treatment	PT
10084461	SARS-CoV-2 carrier	PT
10084480	SARS-CoV-2 test false negative	PT
10084639	SARS-CoV-2 sepsis	PT
10084640	SARS-CoV-2 viraemia	PT
10085080	Congenital COVID-19	PT
10085492	Vaccine derived SARS-CoV-2 infection	PT
10085493	SARS-CoV-2 RNA	PT
10085495	SARS-CoV-2 RNA increased	PT
10085496	SARS-CoV-2 RNA decreased	PT
10085497	SARS-CoV-2 RNA fluctuation	PT
10085503	Post-acute COVID-19 syndrome	PT
10085850	Multisystem inflammatory syndrome in adults	PT
10086091	Multisystem inflammatory syndrome	PT
10086158	Thrombosis with thrombocytopenia syndrome	PT
10086861	Breakthrough COVID-19	PT

GLPG0634-CL-MACE, 20DEC22:15:49

## 1. LIST OF ABBREVIATIONS AND DEFINITIONS OF TERMS

Abbreviation	Definition
AM	Arithmetic mean
%AUC extrap	Percentage of extrapolated AUC (%AUC t-∞ ), $(1 - [AUC_{0-t} / AUC_{0-inf}]) * 100$
AUC 0-tau	Area under the concentration-time curve within dosing interval, calculated by linear up/log down trapezoidal method.
BLQ	Below the lower limit of quantification
C max	Maximum observed plasma concentration
CD	Crohn's disease
CL ss /F	Apparent total body clearance at steady state
C tau	The concentration in plasma at the end of a dosing interval
CV%	Percentage coefficient of variation
GM	Geometric mean
H	Hour
IBD	Inflammatory bowel disease
(IL)-6	Interleukin
JAKs	Janus kinases
LLOQ	Lower limit of quantification
Max	Maximum
Min	Minimum
MR cmax	Metabolic ratio of C max
MR ctau	Metabolic ratio of C tau
MR auctau	Metabolic ratio of AUC 0-tau
PD	Pharmacodynamics

---

Abbreviation	Definition
PK	Pharmacokinetic(s)
Q1	1 st quartile
Q3	3 rd quartile
RA	Rheumatoid arthritis
SD	Standard deviation
T max	Time of the maximum observed plasma concentration
TYKs	Tyrosine kinases
UC	Ulcerative colitis

---

## 2. INTRODUCTION

This Pharmacokinetic Analysis Plan (PKAP) for GS-US-419-3895 study has been developed according to the study design described in the study protocol Amendment 9 dated on 02 December 2021 with the purpose of establishing a framework for pharmacokinetic (PK) analysis in which answers to the protocol objectives may be obtained in a rigorous fashion, without bias or analytical deficiency.

The purpose of this plan is two-fold:

- To determine the types of analyses and presentations of data that will form the basis for conclusions to be reached;
- To define in detail how the data will be handled and analyzed, adhering to commonly accepted standards and practices of PK and biostatistical analysis in the pharmaceutical industry and QPS SOPs.

The PK parameters and statistical results outlined herein will be reported in a PK Section that will be included to the Clinical Study Report (CSR).

### 3. STUDY BACKGROUND

Crohn's disease (CD) is a relapsing and remitting form of inflammatory bowel disease (IBD) that causes gastrointestinal signs and symptoms of diarrhea, abdominal pain, weight loss, and the passage of blood or mucous per rectum. The inflammation of CD can involve the mucosal surface of the gastrointestinal tract and penetrate through the full thickness of the gastrointestinal wall, including the serosal surface. Crohn's disease is characterized by phenotype and location of involved bowel. The phenotypes include inflammatory, stricturing, and penetrating subtypes. Stricture formation can result in intestinal obstruction requiring surgical management. Over time, patients with repeated surgeries are at risk for developing short bowel syndrome and/or intestinal failure.

Janus kinases (JAKs) are intracellular cytoplasmic tyrosine kinases (TYKs) that transduce cytokine signaling from membrane receptors through signal transducer and activator of transcription (STAT) to the nucleus of cells. JAK inhibitors block the signaling of various cytokines, growth factors, and hormones, including the proinflammatory cytokine interleukin (IL)-6. Four different types of JAKs are known, JAK1, JAK2, JAK3, and TYK2 which interact with different sets of membrane receptors. Inhibition of JAKs is a promising therapeutic option for a range of inflammatory conditions including rheumatoid arthritis (RA) and CD.

Filgotinib (GS-6034, formerly known as GLPG0634) is a potent and selective inhibitor of JAK1. Filgotinib is approved in the European Union (EU), Japan, and Great Britain for treatment of moderate to severe active RA in adult patients. It is also approved for the treatment of moderately to severely active ulcerative colitis (UC) in adults in the EU, and is currently under regulatory review for the treatment of UC in Japan and Great Britain. The compound has shown good preliminary efficacy in CD patients in Phase 2 studies.

In humans, filgotinib is metabolized to form one major active metabolite, GS-829845. Though the potency of this metabolite is lower than the parent molecule, the overall exposure and peak plasma concentration in humans is higher than seen in all tested animal species. As a consequence, dedicated pharmacology and toxicology studies have been performed with GS-829845. Results from pharmacodynamics (PD) testing in healthy volunteers suggest that the clinical activity of filgotinib could result from the combination of the parent molecule and the metabolite.

For further information on filgotinib, refer to the current Investigator's Brochure (IB).

#### **4. PKAP OBJECTIVE**

- To assess the PK characteristics of filgotinib and its metabolite GS-829845.

## 5. SUMMARY OF STUDY DESIGN

These are combined Phase 3 double-blind, randomized, placebo-controlled studies to evaluate the efficacy and safety of filgotinib in the induction and maintenance of clinical remission, as well as, endoscopic response in subjects with moderately to severely active CD.

Subjects who are biologic-naïve or biologic-experienced will be enrolled in Cohort A and subjects who are biologic-experienced will be enrolled in Cohort B, respectively. Treatment assignments will be randomized within each Cohort.

### **Treatment Regimen (Cohorts A and B Induction Studies)**

Subjects who meet protocol eligibility criteria will be assigned to the respective Cohort and subsequently randomized in a blinded fashion in a 1:1:1 ratio to 1 of 3 treatments as follows:

**Treatment 1:** filgotinib 200 mg oral tablet and placebo-to-match (PTM) filgotinib 100 mg oral tablet, once daily

**Treatment 2:** filgotinib 100 mg oral tablet and PTM filgotinib 200 mg oral tablet, once daily

**Treatment 3:** PTM filgotinib 200 mg oral tablet and PTM filgotinib 100 mg oral tablet, once daily

Note: US and Korea males who have not failed at least two biologic therapies (any TNF $\alpha$  antagonist and vedolizumab) will be randomized in a 1:1 ratio to either filgotinib 100 mg or matching placebo.

The sparse PK samples at Week 4 are collected pre-dose, and post-dose (at least 30 minutes and up to 3 hours after study drug dosing). For this visit, it is preferred that study drug dosing is done in clinic. The PK sample at Weeks 26 can be collected at any time without regard to dosing. The PK sample at Weeks 10 and 58 are collected at pre-dose (within 2 hours prior to dosing).

The optional PK substudy will be performed in a subset of subjects (approximately 16 subjects on 200 mg treatment and 16 subjects on 100 mg treatment in the substudy) who provide a separate informed consent. In the PK substudy, the daily dose of study drug should be administered under supervision in the clinic (at one visit between Week 2 and Week 10, inclusive), and the PK substudy will have additional plasma PK samples at any single visit from Week 2 to Week 10, collected pre-dose, and at 0.5, 1, 2, 3, 4 and 6 hours after supervised dosing in the clinic. If a sub-study PK sample is scheduled to be collected at the same time as a sparse PK sample, only one sample should be collected.

For all visits with PK sampling, the time of dose taken prior to and on the day of visit will be noted in the eCRF. Plasma concentrations of filgotinib and its metabolite (GS-829845) will be analyzed.

## 6. PHARMACOKINETIC ANALYSIS PLAN

### 6.1. PK Substudy Analysis Set

The primary analysis set for intensive PK analyses will be the PK substudy analysis set for each Induction Study (Cohorts A and B), which includes all subjects in the Safety Analysis Set from the corresponding Induction Study who have enrolled into the PK substudy, and have dense concentration data to provide interpretable results for the specific parameters of interest for the analyte under evaluation.

The primary analysis set for general PK analyses will be defined separately for each individual study (Cohort A Induction Study, Cohort B Induction Study, and Maintenance Study). For each study, the PK analysis set includes all subjects in the corresponding Safety Analysis Set who have at least 1 non-missing plasma concentration data for filgotinib and/or its metabolite GS-829845.

### 6.2. Pharmacokinetic Parameters Estimation

The plasma PK parameters for filgotinib and its metabolite (GS-829845) will be derived by non-compartmental analysis of the plasma concentration-time profiles based on actual blood sampling times [h] (relative to the corresponding administration time) rounded to two decimal digits and negative pre-dose times set to zero. The plasma PK parameters will be computed using Phoenix WinNonlin 6.3 or higher. The nominal times will be used to present in the individual concentration listings or tables and the mean concentration-time figures.

The following plasma PK parameters of filgotinib and its metabolite (GS-829845) will be calculated as data allows. The definition for each PK variable is listed in the following tables:

$C_{max}$	The maximum observed plasma concentration
$T_{max}$	The time to reach $C_{max}$
$C_{tau}$	The concentration in plasma at the end of a dosing interval
$AUC_{0-tau}$	Area under the concentration-time curve within dosing interval, calculated by linear up/log down trapezoidal method. A 24 hour data point will be based on imputation of the predose value of filgotinib and its metabolite (GS-829845).
$CL_{ss}/F$	Apparent total body clearance at steady state, calculated as Dose/ $AUC_{0-tau}$ , on steady state, for parent compound only
MR $c_{max}$	Metabolic ratio of GS-829845 $C_{max}$ / filgotinib $C_{max}$ * (425.51/357.43)
MR $c_{tau}$	Metabolic ratio of GS-829845 $C_{tau}$ / filgotinib $C_{tau}$ * (425.51/357.43)
MR $auctau$	Metabolic ratio of GS-829845 $AUC_{0-tau}$ / filgotinib $AUC_{0-tau}$ * (425.51/357.43)

The substudy PK analysis population will be used for the analyses. Individual subject listings will be provided. For substudy PK analysis, mean and individual plasma concentration-time

profiles for filgotinib and its metabolite (GS-829845) will be presented graphically for each treatment.

The measured individual plasma concentrations of filgotinib and its metabolite (GS-829845) will be used to directly obtain  $C_{\max}$  and  $T_{\max}$  for substudy PK analysis.

The concentration in plasma at the end of a dosing interval ( $C_{\tau}$ ), where tau is 24 h, was also determined. To estimate  $AUC_{0-\tau}$ , the concentration observed in the predose sample (collected at steady-state) will be assumed as the same 24h post-dose.

For general PK analysis, descriptive statistics for plasma concentrations of filgotinib and its metabolite GS-829845 will be listed and summarized per timepoint and per treatment for Cohort A, Cohort B, and maintenance study.

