### 5.3. Dosage and Administration

The study medication will consist of 200 mg and 100 mg filgotinib tablets for oral administration, and PTM 200 mg and 100 mg filgotinib tablets for oral administration.

The following treatments will be evaluated:

- **Treatment 1:** filgotinib 200 mg and PTM filgotinib 100 mg, once daily
- **Treatment 2:** filgotinib 100 mg and PTM filgotinib 200 mg, once daily
- **Treatment 3:** PTM filgotinib 200 mg and PTM filgotinib 100 mg, once daily

Subjects who are non-responders based on the results of the Week 10 assessments will be offered the option to receive open-label filgotinib by entering into the LTE study (GS-US-419-3896). Subjects meeting disease worsening criteria after Week 11 must be discontinued from blinded treatment and will be offered the option to receive open-label filgotinib 200 mg (See Section 3.6, Disease Worsening Criteria), except for US and Korea males who will be offered filgotinib 100 mg unless they have failed at least 2 other biologic therapies (any TNF $\alpha$  antagonist and vedolizumab). Subjects who complete the Week 58 visit will have the option to continue study drug in a blinded fashion in the LTE study.

For missed dose(s) of study medication, subjects should be instructed to take the missed dose(s) of study medication as soon as possible during the same day. If the missed dose is not taken on the original day, then subjects should not take the missed dose and the missed dose should be returned to the study drug bottle. Subjects should be cautioned not to double the next dose (ie, taking the missed dose of study drug with that day's dose).

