### 6.4.4. Pharmacokinetics Assessments

The PK sample at Week 4 is collected post-dose (at least 30 minutes and up to 3 hours after study drug dosing). For this visit, it is preferred that study drug dosing is done in clinic. The PK sample at Weeks 26 can be collected at any time without regard to dosing. The PK sample at Weeks 10 and 58 are collected at pre-dose (within 2 hours prior to dosing).

Subjects who consent to the optional PK substudy will have additional plasma PK samples at any single visit from Week 2 to Week 10, collected pre-dose, and at 0.5, 1, 2, 3, 4 and 6 hours after supervised dosing in the clinic. If a sub-study PK sample is scheduled to be collected at the same time as a sparse PK sample, only one sample should be collected.

For all visits with PK sampling, the time of dose taken prior to and on the day of visit will be noted in the eCRF. Plasma concentrations of filgotinib and its metabolite (GS-829845) will be analyzed.

CCI

CCI

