**6.4. Statistical Evaluations of PK Parameters**

For each individual study (Cohort A Induction Study, Cohort B Induction Study and Maintenance Study), plasma concentrations of filgotinib and its metabolite GS-829845 will be listed and summarized by treatment using descriptive statistics (eg, sample size, arithmetic mean, geometric mean, % coefficient of variation, standard deviation, median, minimum, and maximum).

For the subjects at the substudy, individual concentrations and PK parameters of filgotinib and its metabolite GS-829845 will be listed. Mean concentrations and PK parameters of filgotinib and its metabolite GS-829845 will be summarized descriptively. Individual and mean concentration-time profiles will be presented on semi-logarithmic and linear formats as mean  $\pm$  SD and median (Q1, Q3) by treatment.

For descriptive statistics of pharmacokinetic parameters and concentration data, sample size, arithmetic mean, geometric mean, % coefficient of variation, standard deviation, median, 1st quartile [Q1] (for concentration data only), 3rd quartile [Q3] (for concentration data only), minimum, and maximum, will be given.

Plasma concentrations for the subjects at each individual study and substudy will be listed by subject and nominal sampling time and summarized by nominal sampling time and treatment using descriptive statistics. Similarly, calculated plasma PK parameters for substudy will be listed by subject and summarized by treatment using descriptive statistics.

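### PKAP 6.2 copies the predose concentration to 24 h with no condition on time since the previous dose, which biases AUC0-tau, Ctau, CLss/F, MRctau and MRauctau (not MRcmax) in substudy subjects whose last interval was far from 24 h

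*SAP*

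**What the plan says.** PKAP 6.2 takes the 24 h point from the predose sample for both filgotinib and GS-829845: "the concentration observed in the predose sample (collected at steady-state) will be assumed as the same 24h post-dose". Substudy samples are "collected pre-dose, and at 0.5, 1, 2, 3, 4 and 6 hours after supervised dosing in the clinic", so the last measured point is at 6 h. Sampling times are taken relative to the supervised dose, and negative predose times are set to zero. AUC0-tau is then a linear-up/log-down trapezoid over 24 h, CLss/F is dose divided by AUC0-tau (parent only), and MRauctau is the ratio of the two AUCs. Ctau is described only by "where tau is 24 h, was also determined". Cmax and Tmax come directly from measured concentrations.

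Protocol 5.3 prescribes once-daily dosing without a clock time. A subject who forgets a dose should "take the missed dose(s) of study medication as soon as possible during the same day". Protocol 6.4.4 requires that "the time of dose taken prior to and on the day of visit will be noted in the eCRF". The only predose window concerns the sparse samples: "The PK sample at Weeks 10 and 58 are collected at pre-dose (within 2 hours prior to dosing". It looks forward to the next dose, not back to the last one. PKAP 6.4 has concentrations "summarized by nominal sampling time and treatment using descriptive statistics".

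PKAP 6.3 treats samples as missing when a sampling or dosing time was not recorded, lets the pharmacokineticist exclude subjects with significant protocol deviations or violations, and has an explicit rule for vomiting. No rule uses the recorded previous dose time.

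**The concern.** Of the 24 h in AUC0-tau, 18 h (6 to 24 h) hang on one imputed value. That value equals C24 only if the previous dose was taken about 24 h before the predose sample. Neither document requires this. A subject who takes a forgotten dose at 21:00 and has supervised dosing at 09:00 has followed the protocol, yet the predose value is a 12 h concentration. The exclusions in PKAP 6.3 do not reach this subject: the times are recorded, there is no deviation and no vomiting.

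At stake are five of the derived substudy parameters. PK is a secondary objective in each study, and both documents leave room for exposure-response work. Irregular dosing times would appear as differences in exposure and clearance between subjects, and would distort the parent-to-metabolite comparison because the two analytes need not decline at the same rate.

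**Working it through.** The plan gives no expected AUC, Ctau or error figure, so there is nothing to reproduce. The check applies the PKAP's own rule to profiles with a known answer.

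**Inputs from the documents.** tau = 24 h; samples at 0, 0.5, 1, 2, 3, 4 and 6 h; 24 h value = predose value; linear-up/log-down trapezoid; CLss/F = dose/AUC0-tau; about 16 subjects per dose (PKAP 5). The only half-lives given are 4 h in rats and 5 h in dogs (Protocol 1.2.2.3).

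**Assumptions.** One compartment with oral absorption, ka 1 to 2/h, parent half-life 4, 5 or 7 h. Dosing is every 24 h until the last interval before the supervised dose, which is g hours.

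**Ctau.** Once absorption is over, with k = ln 2/half-life, superposition gives

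imputed C24 / own C24 = e^(k(24−g)) / (1 − e^(−24k) + e^(−kg)).

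- g = 24: the ratio is exactly 1, so the rule is sound at a 24 h interval.
- g = 12, half-life 4 h: 8 / (1 − 0.0156 + 0.125) = 7.21.
- g = 12, half-life 7 h: 3.28 / (1 − 0.0929 + 0.3048) = 2.71.
- g = 20, half-life 4 h: 2 / (1 − 0.0156 + 0.0313) = 1.97.
- g = 28, half-life 4 h: 0.5 / (1 − 0.0156 + 0.0078) = 0.50.

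**AUC0-tau and CLss/F.** Two comparators are needed. The first keeps the same irregular profile and trapezoid but uses the subject's own C24; this isolates the imputation. The second is the steady-state AUC, which CLss/F assumes. Ranges are over half-lives 4, 5 and 7 h and ka 1 to 2/h.

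| Ratio | g = 12 h | g = 20 h | g = 24 h | g = 28 h |
|---|---|---|---|---|
| Ctau / own C24 | 2.71–7.21 | 1.42–1.97 | 1.00 | 0.50–0.69 |
| AUC0-tau / same trapezoid with own C24 | 1.257–1.386 | 1.075–1.092 | 1.000 | 0.929–0.939 |
| AUC0-tau / steady-state AUC | 1.50–1.58 | 1.09–1.13 | 0.99 | 0.90–0.92 |
| CLss/F / true CL/F | 0.63–0.67 | 0.89–0.92 | 1.01 | 1.09–1.12 |

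At 12 h the total against steady state is +50% to +56% at half-lives of 4 and 7 h, and peaks at +58% at 5 h. It splits into the two parts: for a 4 h half-life and ka 1/h, 1.556 = 1.386 (imputation) × 1.123 (carry-over from the short interval). The true exposure on that day is already 12% to 24% above steady state.

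**Metabolite and ratios.** With an assumed metabolite half-life of 15 to 25 h, a 12 h gap multiplies its imputed Ctau by 1.15 to 1.38 and its AUC by 1.05 to 1.11. Because the parent moves much more, MRctau falls to 0.27 to 0.45 of true and MRauctau to 0.80 to 0.85 (parent 5 to 7 h, metabolite 20 h). MRcmax does not use the 24 h point and is unchanged.

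**Effect on a group of 16.** Suppose 15 subjects are at steady state and one has a 12 h gap. That subject's Ctau is e^(12k) = 3.28 to 8 times the steady-state value, so the arithmetic mean rises by (3.28 − 1)/16 = 14% to (8 − 1)/16 = 44%. Mean AUC0-tau rises by 0.50/16 = 3.1% to 0.58/16 = 3.6%.

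**The case against.** Several points on the other side stand.

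- A reader might attribute the whole +50% to +58% to the imputation. That is wrong: a subject dosed 12 h earlier really has more drug on board that day. The rule accounts for +26% to +39%.
- A reader might conclude that all the metabolic ratios are wrong. MRcmax rests on measured Cmax.
- A reader might extend the point to a skipped day. Protocol 7.7.1 counts a missed dose among medication errors, so this is not a clean example of compliance, and the deviation clause in PKAP 6.3 might reach it.
- A reader might say the Week 10 and Week 58 predose values share the fault. Nothing is imputed there and no parameter is derived from them. They are observed concentrations, correctly labelled predose whatever the gap. A problem arises only if they are read as 24 h troughs.
- The plan is not without discretion. PKAP 6.1 asks for data that can be interpreted for the parameter in question, and PKAP 6.2 calculates parameters where the data permit. With the previous dose time on file, the pharmacokineticist could withhold a parameter. What is missing is a stated criterion, so any such exclusion would be decided case by case, possibly with the concentrations in view.
- No document supports a particular window, and one of 20 to 28 h would still leave Ctau off by up to twofold.

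These points limit the scope. They do not supply the missing condition.

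**Conclusion.** The concern holds for the five parameters that use the 24 h point, in substudy subjects whose previous dose was well away from 24 h before the predose sample. It is large for Ctau and MRctau, moderate for AUC0-tau, CLss/F and MRauctau at a gap near 12 h, and small for the AUC-based parameters within 4 h of 24 h (under 10% from the rule, up to about 13% against steady state).

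The sizes rest on assumed human half-lives and a one-compartment model. That Ctau is the imputed value is inferred from the absence of a 24 h sample. The frequency of irregular gaps is unknown, and the documents do not support a claim that they are common. The effect is confined to descriptive PK in about 32 subjects (16 per dose) and any exposure-response work built on it. No efficacy comparison or type I error is touched. The change is worth making because it is cheap, but the trial's conclusions do not depend on it.

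**What to change.** In PKAP 6.2, derive the actual time from the previous dose to the predose sample, and use the predose value as C24 only inside a window fixed before the concentrations are reviewed. One choice is 20 to 28 h for AUC0-tau, CLss/F and MRauctau, with a narrower window for Ctau and MRctau. At 22 to 26 h, for example, the formula above with a 4 h half-life gives 1.41/1.006 = 1.41 and 0.707/0.995 = 0.71, against 1.97 and 0.50 at 20 and 28 h. Outside the window, set the affected parameters to missing and list the concentrations with the actual interval. MRcmax, Cmax and Tmax need no change.

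For the Week 10 and Week 58 predose summaries, list the actual time since the previous dose, and apply the window only if the values are to be interpreted as troughs.

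The cost is a few sentences in the PKAP and one derived variable from data already in the eCRF. The downside is that a few profiles drop out of the parameter summaries, and more do so for Ctau and MRctau if their window is narrower. Dosing instructions and data collection stay as they are.
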